6.1.2. Part B

6.1.2.1. Open-label Titration

The planned titration schedule for PRAX-944 is as follows:

- 20 mg QAM for 3 days
- 40 mg QAM for 4 days
- 60 mg QAM for 7 days
- 80 mg QAM for 7 days
- 100 mg QAM for 7 days
- 120 mg QAM for 14 days

[figure not shown]

Table 4: Study Drug Information

ARM Name	Open-Label Part A	Open-label Part B	Double-blind PRAX-944	Double-blind Placebo
Intervention Name	PRAX-944			Placebo
Type	Drug			Placebo
Dose Formulation	Modified-release tablet			Tablet
Unit Dose Strength(s)	20 mg			Placebo
Dosage Level(s)	
 • 20 mg QAM Day 1 through Day 7 • 40 mg QAM Day 8 through Day 14 	
 • 20 mg QAM Day 1 through Day 3 • 40 mg QAM Day 4 through Day 7 • 60 mg QAM Day 8 through Day 14 • 80 mg QAM Day 15 through Day 21 • 100 mg QAM Day 22 through Day 28 • 120 mg QAM Day 29 through Day 42 	
 • 120 mg or highest tolerated dose QAM Day 43 through Day 56 	
 • Placebo QAM Day 43 through Day 56
Route of Administration	Oral			
				None
Sourcing	Provided centrally by the Sponsor			
Packaging and Labeling	Study drug will be provided in pre-packaged containers. Each container will be labeled as required per country requirements.			

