5 ANALYSIS METHODS

Analysis will be carried out using SAS® (version 9.4 or newer, SAS Institute Inc, Cary, NC). Templates for the summary tables, figures, and participant data listings will be available separately. Data listings will include all data recorded for all enrolled participants; where captured, data entered for screen failure participants will be flagged in the listings.

For all data displays, separate summaries will be generated for each part and phase (open-label titration and double-blind randomized withdrawal) of the clinical trial.

- Part A: All summaries except those for adverse events will use a single "PRAX-944 Overall" column. Summaries of adverse events will use the following columns: "PRAX-944 20 mg qAM", "PRAX-944 40 mg qAM ", and "PRAX-944 Overall".
- Part B: Summaries of disposition and PK will be presented for all of Part B (i.e., not by phase) and will use a single "PRAX-944" column.
- Part B Open-label Titration: Summaries of demographics, baseline characteristics, medical history, prior and concomitant medications, study drug exposure, efficacy, and all safety except adverse events will include a "PRAX-944 Overall" column. Summaries of adverse events will include columns for "PRAX-944 20 mg qAM", "PRAX-944 40 mg qAM ", "PRAX-944 60 mg qAM ", "PRAX-944 80 mg qAM ", "PRAX-944 100 mg qAM ", "PRAX-944 120 mg qAM ", and "PRAX-944 Overall".
- Part B Randomized Withdrawal: Summaries of demographics, baseline characteristics, medical history, prior and concomitant medications, study drug exposure, efficacy, and all safety except adverse events will include the columns "Placebo" and "PRAX-944" for the randomized withdrawal phase. Summaries of adverse events will include columns for "Placebo" and "PRAX-944".

Descriptive statistics for continuous data will include number of participants (n), mean, standard deviation (SD), median, minimum, and maximum. Summaries of change from baseline variables will include only participants who have both a baseline value and corresponding value at the timepoint of interest. Descriptive statistics for categorical data will include frequency and percentage. Where appropriate, descriptive statistics may be presented with 95% confidence intervals (CIs).

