5.8.1 AEs

The overall incidence of participants having at least one AE in each of the following categories will be summarized by treatment group and dose level, as defined in [Section 5](#):

- Any TEAE
- Any serious adverse event (SAE)
- Any AE leading to death
- Any AESI
- Any TEAE leading to study drug withdrawal
- Any related TEAE

The overall AE incidence summary, as well as summaries identified in subsequent sections, will be reported by part and phase. Part A and Part B open-label titration phase summaries will be based on the safety analysis set. Part B double-blind randomized withdrawal phase summaries will be based on the randomized withdrawal analysis set.

All AE data will be listed by study part and participant. Separate listings will be presented for SAEs, AEs leading to death, and TEAEs leading to study drug withdrawal.

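### Part B open-label AE percentages by dose level rest on planned windows of 3 to 14 days, with no participant-days or exposure-adjusted rate beside them

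*SAP*

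**What the plan says.** SAP section 5 (Analysis Methods), in its entry for Part B open-label titration, states that "Summaries of adverse events will include columns for" 20, 40, 60, 80, 100 and 120 mg and PRAX-944 overall. (The same words recur in the entry for the randomized withdrawal phase, where both arms have 14 days; that phase is not at issue.) SAP 5.8.1 adds that the incidence of participants with at least one AE "will be summarized by treatment group and dose level". Categorical data are shown as frequency and percentage, and SAP 5.8.1.1 counts a participant once per SOC and preferred term.

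SAP 4.10.1 reports each AE only under the dose level at which it began. Each column therefore counts onsets within that dose's window. Protocol 6.1.2.1 sets the windows. The schedule opens with "20 mg QAM for 3 days" and closes with "120 mg QAM for 14 days"; in between, the 40 mg step lasts 4 days and the 60, 80 and 100 mg steps last 7 days each.

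SAP 4.8 derives exposure duration by dose level as last dose date minus first dose date plus 1. Nothing in SAP 5.8 uses that duration for AEs. The SAP also does not say whether a column's denominator is the whole safety set or only those who reached that dose. Safety is descriptive, with no hypothesis tests (SAP 5.8).

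**The concern.** A percentage of participants with an event grows with the time watched. The longest planned window (14 days) is 4.7 times the shortest (14/3), and the longest belongs to the highest dose while the shortest belongs to the lowest. A reader who looks across the columns cannot tell how much of a rise reflects dose and how much reflects days at risk.

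Safety and tolerability is the primary objective of Part B (Protocol 3.2), and the trial is meant to inform later controlled studies (SAP 2.3). The dose-level columns are the SAP's own choice of layout, so they will be read side by side.

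**Working it through.** **Plan's own AE figure.** SAP 2.3 gives 10 participants an 80% chance of showing at least one AE with 15% incidence: 1 − 0.85^10 = 0.803. It reproduces. The documents attach no period to the 15%; below it is assumed to apply over 42 days and serves as the low case.

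**Inputs.** Windows of 3, 4, 7, 7, 7 and 14 days (Protocol 6.1.2.1), which sum to 42. N is about 12, up to 24 (Protocol 5.1.2). The daily AE rate is not given, so a range of 42-day incidences P is assumed.

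**Formula.** With a constant daily hazard h and no dose effect, h = −ln(1 − P)/42, and the expected percentage in a column of w days is 1 − exp(−h × w).

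Example, P = 50%: h = 0.6931/42 = 0.0165. At 20 mg, 1 − exp(−0.0165 × 3) = 4.8%. At 120 mg, 1 − exp(−0.0165 × 14) = 20.6%. The ratio is 4.3.

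| Assumed P over 42 days | h per day | 20 mg | 40 mg | 60, 80, 100 mg (each) | 120 mg | Ratio 120/20 |
|---|---|---|---|---|---|---|
| 15% | 0.0039 | 1.2% | 1.5% | 2.7% | 5.3% | 4.6 |
| 50% | 0.0165 | 4.8% | 6.4% | 10.9% | 20.6% | 4.3 |
| 80% | 0.0383 | 10.9% | 14.2% | 23.5% | 41.5% | 3.8 |
| 95% | 0.0713 | 19.3% | 24.8% | 39.3% | 63.2% | 3.3 |

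Ratios are from unrounded percentages. The limit for rare events is 14/3 = 4.7.

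**Would it show in a small table?** Treating the columns as independent, the chance that the observed 120 mg percentage exceeds the 20 mg percentage with no dose effect is, at n = 12, 43% for P = 15%, 81% for P = 50% and 94% for P = 80%. At n = 24 it is 63%, 93% and 99%. For a rare term at n = 12 (P = 15%) the expected counts are only 0.1 at 20 mg and 0.6 at 120 mg.

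**With participant-days.** At n = 12 and full titration the columns hold 12 × 3 = 36, 48, 84, 84, 84 and 168 participant-days. Under a constant hazard the expected rate of first events per 100 participant-days at risk is the same in every column: 0.39, 1.65 and 3.83 for P = 15%, 50% and 80%. The ratio becomes 1.0.

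**The opposite case.** Suppose instead that 20% of participants have an event on the first day of every step and nobody has one later. The percentages are flat at 20%. Days at risk per participant are 0.2 × 1 + 0.8 × 3 = 2.6 at 20 mg and 0.2 × 1 + 0.8 × 14 = 11.4 at 120 mg. The rates are 0.20/2.6 = 7.7 and 0.20/11.4 = 1.75 per 100 participant-days, a spurious 4.4-fold fall.

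**The exposure formula.** One return to a lower dose is allowed (Protocol 6.6). Illustration: 80 mg on Days 15 to 21, 100 mg on Days 22 to 24, 80 mg on Days 25 to 42. Actual days at 80 mg are 7 + 18 = 25. The SAP 4.8 formula gives 42 − 15 + 1 = 28, which counts the three days at 100 mg as well.

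**The case against.** The plan makes no dose comparison. Safety is descriptive, no dose-response analysis of AEs is specified, and the overall column does not depend on how the 42 days are divided. The Part B objective names safety and tolerability without mentioning dose level.

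The constant hazard is an assumption that the documents do not support. Protocol 2.4 reports nausea and vomiting after a single 60 mg dose and says that most side effects were short-lived, which fits events clustered after a step up. In that case window length matters little, and a rate would mislead in the other direction by as much, as the opposite case shows. Dose reductions shorten the upper windows and lengthen the lower ones. Table templates are held separately and may already show exposure.

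Most of this stands, and it limits the claim. It does not remove it. The absence of tests is no protection, because the distortion would lie in the descriptive percentage itself. The SAP derives exposure by dose level but does not require it to appear in the AE tables, and unseen templates cannot be relied on for that.

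**Conclusion.** The point holds in a conditional form. The dose-level AE tables of the Part B open-label phase show percentages over unequal planned time at risk, with no measure of that time beside them. Under a constant daily rate, no dose effect and full titration, the expected percentage would rise about 3.3- to 4.7-fold from 20 to 120 mg. The pattern is one of steps: a small rise from 20 to 40 mg, larger ones from 40 to 60 mg and from 100 to 120 mg, and nothing between 60 and 100 mg. It matters mainly for any TEAE and common terms.

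A reader might infer three stronger things that the documents do not support. One is that the table is bound to show a false dose-response or to overstate risk at 120 mg; that needs the constant hazard, which is assumed. Another is that AE risk by dose is the primary objective; the dose columns come from the table layout. The third is that rates should replace percentages for dose comparisons; if events cluster after escalation, that would understate the risk at 120 mg relative to 20 mg.

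**What to change.** In the dose-level AE tables for Part B open-label titration, keep the percentages and add three items per column:

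- the number of participants exposed at that dose;
- the actual participant-days at that dose, summed over separate segments rather than taken as last dose minus first dose plus 1;
- the exposure-adjusted incidence rate, as participants with a first event per 100 participant-days at risk.

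Add a footnote that neither measure alone isolates dose, because a single-sequence titration confounds dose with time and adaptation, and that the two should be read together.

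The cost is a few rows or header lines from dosing and AE dates that the eCRF already holds; no planned output is lost. The downside is that the rate assumes a roughly constant hazard within each step and is imprecise at 20 mg, where 12 participants give only about 36 participant-days.

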5.1 Participant Disposition

All participants in the enrolled analysis set will be included in disposition summaries. The number of participants screened, screen failed, randomized, completed, and discontinued from the study, as well as reason for discontinuation, will be summarized by treatment group and overall. The number of participants in each analysis set will also be summarized. All disposition data will be listed by participant.

5.2 Protocol Deviations

Major protocol deviations will be summarized by treatment group and overall using the safety analysis set. All inclusion/exclusion criteria and protocol deviation data will be listed by participant.

5.3 Demographics and Other Baseline Characteristics

Descriptive summaries of the demographic and other baseline characteristics will be provided by treatment group and overall using the safety analysis set and randomized withdrawal safety analysis set. These tabulations will include the following variables:

- Age
- Sex
- Ethnicity
- Child-bearing potential
- Race
- Dominant Hand
- Height (cm)
- Weight (kg)
- BMI (kg/m²)
- Baseline TETRAS upper limb score category (<10, ≥10)

All demographics and other baseline characteristics data will be listed by participant.

5.4 Medical History

Descriptive summaries of medical history will be provided by treatment group and overall using the safety analysis set and randomized withdrawal safety analysis set. Medical history will be displayed by MedDRA system organ class (SOC) and preferred term. All medical history data will be listed by participant.

5.5 Essential Tremor Medical History

Descriptive summaries of essential tremor medical history will be provided by treatment group and overall using the safety analysis set and randomized withdrawal safety analysis set. ET medical history data will also be listed by participant.

5.6 Prior and Concomitant Medications

[figure not shown]
[figure not shown]
Descriptive summaries of prior medications will be provided by treatment group and overall using the safety analysis set and randomized withdrawal safety analysis set. Both prior and concomitant medications will be displayed by Anatomical Therapeutic Chemical (ATC) classification level 3 and preferred term. All prior and concomitant medication data will be listed by participant.

[figure not shown]

5.7 Efficacy Analyses

Unless otherwise indicated, all efficacy data will be analyzed by part using the full analysis set. In summaries of change from baseline variables, only participants with both baseline and change from baseline values will be included. Summaries based on the full analysis set will include all timepoints, regardless of period, and will include changes from baseline where appropriate. Unless stated otherwise, summaries of efficacy endpoints will additionally include displays based on the randomized withdrawal analysis set, including randomization baseline and change from randomization, where applicable, to report data collected after receipt of randomized treatment. Summaries based on the randomized withdrawal set will also include open-label titration results and changes from baseline. All efficacy data will be listed; the listings will include all reported and derived values as well as rater ID, where applicable. Analysis of TETRAS scores may be performed for dominant hand only.

5.7.1 Primary efficacy analysis

For Part A, the change from baseline in TETRAS upper limb score to each post-dose timepoint will be analyzed using Mixed Model Repeated Measures (MMRM) methods using the full analysis set. The model will include timepoint as a fixed effect and the baseline TETRAS upper limb score as a covariate. Within subject variability will be modeled using an unstructured covariance pattern. In case of convergence problems, a banded Toeplitz structure for the covariance pattern will be used. Model based point estimates (ie, least square [LS] means), standard error, 95% confidence interval, and p-value will be reported for each timepoint. Reported p-values will test the LS mean for each timepoint versus zero. Similar MMRM methods will be used for the open-label titration phase of Part B. The SAS code to be used for the MMRM analysis is provided below:

Line-plots of the estimated LS means will be used to graphically illustrate the TETRAS upper limb scores over time.

For Part A and both phases of Part B, the TETRAS upper limb score as measured by the clinician will be summarized using descriptive statistics for the reported, change from baseline, and change from randomization (where applicable) values by timepoint. TETRAS upper limb data will be listed by study part, participant, and visit.

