9.1. Sample Size Determination

The sample size of each part (up to 12 participants) is a convenience sample. The sample size was not selected according to any statistical power calculation. Instead, the sample size was determined according to feasibility and is thought to provide sufficient efficacy and safety data to inform the development of future controlled studies with PRAX-944 in participants with ET. Part B sample size may be increased to up to 24 participants to ensure inclusion of a broad range of tremor severity. In the open-label phases of the trial (Part A and Part B, open-label titration), a sample size of at least 10 participants would provide an 80% probability of observing at least 1 AE with an underlying incidence of 15% or greater. In addition, 10 participants should also provide approximately 80% power to detect an effect size of 1.0 on the primary endpoint of change from Baseline in TETRAS Upper Limb score.

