9.3.1. Efficacy Analyses

Reported values and change from baseline values in TETRAS Upper Limb score, TETRAS Performance subscale total and individual scores, TETRAS Upper Limb accelerometer score, TETRAS Upper Limb telehealth score, TETRAS ADL Subscale score, [REDACTED], QUEST total and subscale scores, [REDACTED] will be summarized by time point. In addition, change from baseline scores will also be analyzed using paired t-tests or similar methods. For [REDACTED], reported values will be summarized by time point.

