2.3 Determination of Sample Size

Up to 12 participants are planned to be administered PRAX-944 in Part A. Approximately 12 participants are planned to be administered PRAX-944 in Part B. Up to 12 additional participants may be enrolled at the discretion of the Sponsor to ensure inclusion of a broad range of tremor severity.

The sample size of each part is a convenience sample. The sample size was not selected according to any statistical power calculation. Instead, the sample size was determined according to feasibility and is thought to provide sufficient efficacy and safety data to inform the development of future controlled studies with PRAX-944 in participants with ET. In the open-label phases of the trial (Part A and Part B, open-label titration), a sample size of at least 10 participants would provide an 80% probability of observing at least 1 AE with an underlying incidence of 15% or greater. In addition, 10 participants should also provide approximately 80% power to detect an effect size of 1.0 on the primary endpoint of change from baseline in TETRAS Upper Limb score.

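### The single-arm MMRMs adjust for baseline and test the LS mean change against zero, so whenever change is related to baseline the SE and 95% CI for the population mean change are too narrow

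*SAP*

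**What the plan says.** SAP 5.7.1 analyses change from baseline in the TETRAS upper limb score, the Part A primary endpoint, with a repeated-measures model in the full analysis set. Part A has one treatment group. On the model: "The model will include timepoint as a fixed effect and the baseline TETRAS upper limb score as a covariate". On the covariance: "Within subject variability will be modeled using an unstructured covariance pattern", with a banded Toeplitz fallback. On the output: "Model based point estimates (ie, least square [LS] means), standard error, 95% confidence interval, and p-value will be reported for each timepoint". On the hypothesis: "Reported p-values will test the LS mean for each timepoint versus zero".

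The section extends the approach to the Part B open-label titration. SAP 5.7.2 uses models of the same kind for the accelerometer, combined upper limb, Performance, ADL and QUEST scores. Protocol 9.3.1 describes the analysis more loosely: "change from baseline scores will also be analyzed using paired t-tests or similar methods".

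SAP 5.7.1 introduces its code with "The SAS code to be used for the MMRM analysis is provided below", but the code is absent from the public text. The LSMEANS options and the degrees-of-freedom method therefore cannot be seen.

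**The concern.** Adjusting for baseline is standard when two randomized arms are compared, because the uncertainty in the baseline mean largely cancels in the difference. In one arm tested against zero, nothing cancels it.

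With complete data, the LS mean at the observed mean baseline is simply the raw mean change. The model treats the observed baselines as fixed, so its standard error reflects only the scatter left after regression on baseline. But change contains baseline. In another sample the mean baseline would differ, and the mean change would move with it. With no true mean change in the population, a sample that happens to start high is expected to fall and one that starts low to rise.

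At stake are the standard errors, intervals and p-values of the Part A primary result and of the open-label efficacy results in Part B. SAP 2.3 says these data are meant to inform later controlled studies.

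**Working it through.** **Inputs from the documents.** Part A size: "Up to 12 participants are planned to be administered PRAX-944 in Part A". Part B maximum: "Part B sample size may be increased to up to 24 participants". No alpha is stated; the 95% interval implies two-sided 5%.

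**Inputs assumed.** LS means at the observed mean baseline, and n−2 degrees of freedom. The correlation ρ between baseline and post-baseline scores is not given, so I use 0.5 to 0.9 with equal variances.

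**Step 1. The plan's own figure.** SAP 2.3 and Protocol 9.1 state about 80% power with 10 participants for an effect size of 1.0. A one-sample (paired) t-test with noncentrality √10 × 1.0 = 3.16 on 9 df, two-sided 5%, gives 80.3%. The figure reproduces with the paired t-test, whose SE includes baseline variation.

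**Step 2. The missing term.** Let s² be the common variance and b the slope of change on baseline.

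- True variance of the mean change: (residual variance + b² × Var(baseline))/n
- Variance the model reports: residual variance/n
- With equal variances, b = ρ − 1, Var(change) = 2(1−ρ)s² and residual variance = (1−ρ²)s²
- SE ratio (reported/true) = √[(1−ρ²)/(2(1−ρ))] = √[(1+ρ)/2]

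**Step 3. Type I error.** The statistic is a t variable on n−2 df scaled up by 1/ratio, so the error is 2 × P(t > t_crit × ratio). The critical value is 2.228 at n=12 and 2.074 at n=24. Example: at n=12 and ρ=0.7, 2.228 × 0.922 = 2.054, and the two-sided tail of t on 10 df is 6.7%.

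| ρ | SE ratio | Type I, n=12 | Type I, n=24 | 95% CI coverage, n=12 |
|---|---|---|---|---|
| 0.5 | 0.866 | 8.3% | 8.6% | 91.8% |
| 0.7 | 0.922 | 6.7% | 6.9% | 93.3% |
| 0.8 | 0.949 | 6.1% | 6.2% | 93.9% |
| 0.9 | 0.975 | 5.5% | 5.6% | 94.5% |

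At zero slope (ρ = 1 here) the error is exactly 5.0%.

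**Step 4. Check on the planned model.** A simulated REML MMRM with four post-dose timepoints, a common baseline slope and unstructured covariance (10,000 runs per case) gave 8.3%, 6.8%, 6.1% and 5.4% at n=12. The paired t-test on the same data gave 4.9% to 5.2%.

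**Step 5. A real effect that scales with baseline.** This concerns interval coverage, not false positives. Let the post-baseline SD be k times the baseline SD. The SE ratio is √[k²(1−ρ²)/(1 + k² − 2ρk)].

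- k=0.8, ρ=0.8: √(0.2304/0.36) = 0.80
- k=0.7, ρ=0.8: √(0.1764/0.37) = 0.69

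Over k = 0.7–0.8 and ρ = 0.7–0.8, nominal 95% intervals cover about 83% to 90% at n = 12 to 24. These figures come from the single-timepoint formula and simulation, not from the full MMRM.

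**The case against.** The algebra is hard to dispute. What it implies is open to more argument.

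- **Target of inference.** The reported SE is correct for a narrower quantity, the expected change at this sample's mean baseline. That is true, but zero change at that point is not the same as zero mean change in the population, and the plan does not say it intends the narrower target.
- **Unknown size.** The slope could be small, and at zero slope nothing is wrong. A reader might infer that every open-label p-value is too favourable; the documents do not show that. A non-zero slope is nevertheless likely, because Protocol 8.4.7 expects scores to fluctuate and fluctuation in the baseline score alone produces one.
- **Low stakes.** This is a convenience sample with no stated alpha or decision rule, and efficacy is secondary in Part B. The SAP also tabulates the mean and SD of change, so an unadjusted interval can be recovered. This stands, and it lowers the severity.
- **The protocol's method.** A reader might see an undeclared departure, since SAP 7.1 does not list a move away from paired t-tests. Protocol 9.3.1 allows similar methods and Protocol 9 leaves detail to the SAP, so that reading is not supported.
- **The benchmark is idealised.** Selecting on a score of at least 10 produces regression to the mean, which a paired t-test does not correct. As an illustration, assume a population mean of 11, SD 3, everyone selected at 10 or more, n=12 and no effect. The paired t-test then rejects about 12% of the time at ρ=0.7 and about 10% at ρ=0.8. This is a separate limit of an uncontrolled phase, and the fix below does not remove it.

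**Conclusion.** The concern holds. As written, the open-label single-arm models leave baseline sampling variation out of the SE, so intervals for the population mean change are too narrow whenever change is related to baseline. The type I error is about 5.5% to 8.3% at n=12 for ρ from 0.9 to 0.5, and 5.6% to 8.6% at n=24.

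These figures assume equal variances, LS means at the observed mean baseline and a ρ that the documents do not supply. If the hidden code evaluates LS means differently, the numbers would change. Kenward–Roger degrees of freedom would not by themselves restore the missing term.

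The 83% to 90% figure should not be read as a false-positive rate of 10% to 17%. It applies only when a real effect exists and scales with baseline.

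Severity: should fix. The harm is overstated precision in an exploratory result, not a failed decision rule.

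**What to change.** In every open-label single-arm MMRM, model the scores themselves, with baseline as one of the responses. Use timepoint (including baseline) as the fixed effect and an unstructured covariance, and test each post-minus-baseline contrast against zero. With complete data this matches the paired t-test at each timepoint. Keep baseline as a covariate only in models that compare the randomized arms.

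Simply deleting the covariate is a weaker fix. The two agree only with complete data, and dropout related to baseline is plausible over a 42-day titration. In an illustration with an assumed 30% proportional effect and dropout rising with baseline, the true mean change was −3.6. The no-covariate estimate was about −3.3, and an estimate that used baseline stayed at −3.6.

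A line in SAP 7.1 noting the chosen model would be good practice.

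Cost: the model statement and some SAP wording. Open-label intervals widen by 1/ratio − 1. With no effect that is about 3% at ρ=0.9 (1/0.975) to 15% at ρ=0.5 (1/0.866). If the effect scales with baseline it is up to about 45% (1/0.69).

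The covariance matrix gains a row. With Part A's four post-dose assessments it goes from 4×5/2 = 10 to 5×6/2 = 15 parameters, which is a lot for 12 participants. The fallback needs rewording too, since a banded structure can set correlations with baseline at longer lags to zero.

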5.7.2 Secondary Efficacy Analysis

5.7.2.1 Accelerometer-based upper limb score

For each timepoint, the average score of the two Kinesia ONE assessments will be used for analysis.

For Part A and both phases of Part B, the Kinesia ONE upper limb score will be summarized using descriptive statistics for the reported, change from baseline, and change from randomization (where applicable) values by timepoint. MMRM methods similar to those described in [Section 5.7.1](#) will be used for the change from baseline and change from randomization in Kinesia ONE upper limb scores. Kinesia ONE data will be listed by study part, participant, and visit.

Line-plots of the estimated LS means will be used to graphically illustrate the Kinesia ONE upper limb scores over time.

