5.7.2.3 TETRAS performance subscale total score

For Part A and both phases of Part B, the TETRAS performance subscale total score as measured by the clinician will be summarized using descriptive statistics for the reported, change from baseline, and change from randomization (where applicable) values by timepoint. MMRM methods similar to those described in [Section 5.7.1](#) will be used for the change from baseline and change from randomization in TETRAS performance subscale scores. TETRAS performance subscale data will be listed by study part, participant, and visit.

[figure not shown]

[figure not shown]

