5.7.2.5 TETRAS ADL subscale score

In Part B, the TETRAS ADL subscale total score as measured by the clinician will be summarized using descriptive statistics for the reported, change from baseline, and change from randomization (where applicable) values by timepoint. MMRM methods similar to those described in [Section 5.7.1](#) will be used for the change from baseline and change from randomization in TETRAS ADL subscale scores. TETRAS ADL data will be listed by study part, participant, and visit.

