5.7.2.6 QUEST total and subscale score

[figure not shown]
[figure not shown]
In Part B, the QUEST total and subscale scores will be summarized using descriptive statistics for the reported, change from baseline, and change from randomization (where applicable) values by timepoint. MMRM methods similar to those described in [Section 5.7.1](#) will be used for the change from baseline and change from randomization in QUEST scores. QUEST data will be listed by study part, participant, and visit.

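### In the readable SAP, the clinician-rated TETRAS upper limb score is only described by arm after randomization, and no placebo versus PRAX-944 difference with a confidence interval is stated

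*SAP*

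**What the plan says.** The TETRAS upper limb score is the Part A primary efficacy endpoint and the first-listed Part B secondary efficacy endpoint (SAP 2.1). SAP 5.7.1 analyses its change from baseline in Part A by MMRM: "The model will include timepoint as a fixed effect and the baseline TETRAS upper limb score as a covariate". On inference: "Reported p-values will test the LS mean for each timepoint versus zero". For Part B the extension is: "Similar MMRM methods will be used for the open-label titration phase of Part B". The section then adds: "For Part A and both phases of Part B, the TETRAS upper limb score as measured by the clinician will be summarized using descriptive statistics", and these cover reported values, change from baseline and change from randomization.

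Other measures are treated differently. MMRM methods similar to those of 5.7.1
- "will be used for the change from baseline and change from randomization in Kinesia ONE upper limb scores" (SAP 5.7.2.1);
- "will be used for the change from baseline and change from randomization in TETRAS performance subscale scores" (SAP 5.7.2.3);
- "will be used for the change from baseline and change from randomization in TETRAS ADL subscale scores" (SAP 5.7.2.5);
- "will be used for the change from baseline and change from randomization in QUEST scores" (SAP 5.7.2.6).

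SAP 5.7.2.2 says the same of the combined upper limb score.

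The SAP also sets up the inputs for a comparison of arms: a randomized withdrawal analysis set (3.5), a randomization baseline equal to the Day 42 post-dose value (4), and separate placebo and PRAX-944 columns (5). SAP 5 allows 95% CIs on descriptive statistics as an option. Protocol 9.3 plans summaries by randomized continuation treatment. Protocol 9.3.1 plans paired t-tests or similar methods on change from baseline, which are within-participant analyses.

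**The concern.** The withdrawal phase is the only place in this trial where PRAX-944 is compared with a concurrent, blinded control. SAP 7.1 cites an objective on how long the effect lasts, and upper limb tremor is named in it. Yet the score that leads the efficacy endpoints gets less analysis after randomization than a combined score that contains it and that the SAP itself added.

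At stake is the estimate that randomization makes possible. Change within one arm mixes loss of drug effect with fading of an open-label response and drift in rating. The difference between arms removes whatever the arms share. Protocol 9.1 says the data should inform later controlled studies. A placebo-controlled difference with its precision serves that purpose better than two columns of means.

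**Working it through.** **1. Analyses stated in the readable text**

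| Measure | Model for change from baseline | Model for change from randomization | Between-arm difference with CI |
|---|---|---|---|
| TETRAS upper limb, clinician (5.7.1) | Part A and Part B open-label | none; descriptive by arm | not stated |
| Kinesia ONE (5.7.2.1) | yes | yes, terms not listed | not stated |
| Combined upper limb (5.7.2.2) | yes | yes, terms not listed | not stated |
| Performance total (5.7.2.3) | yes | yes, terms not listed | not stated |
| ADL (5.7.2.5) | yes | yes, terms not listed | not stated |
| QUEST total and subscales (5.7.2.6) | yes | yes, terms not listed | not stated |

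**2. The plan's own figure.** SAP 2.3 gives about 80% power for an effect size of 1.0 with 10 participants. A one-sample t-test has df 9 and noncentrality 1.0 × √10 = 3.16. At two-sided 0.05 (assumed; alpha is not stated) its power is 80.3%, so the figure reproduces. It concerns change within one group and does not describe the randomized comparison.

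**3. Inputs for the two-arm comparison.** Part B has about 12 participants, or up to 24 if enlarged (SAP 2.3), allocated 1:1. That is 6 or 12 per arm if all are randomized and assessed at Day 56 (assumed). Results are in SD of change from randomization, because the documents give no SD.

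**4. Unadjusted 95% half-width** = t(0.975, 2n−2) × √(2/n).
- n = 6: 2.228 × 0.5774 = 1.29
- n = 12: 2.074 × 0.4082 = 0.85
- If only 5 per arm are evaluable, it is 1.46.

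**5. ANCOVA half-width.** Assume equal SDs at Day 42 and Day 56 and correlation r between them. The residual SD relative to the SD of change is √((1+r)/2). Chance imbalance at Day 42 multiplies the half-width by √(1 + 1/(2n−4)), and df is 2n−3. For n = 6 and r = 0.5: 2.262 × 0.5774 × 0.8660 × 1.0607 = 1.20. Simulation of 200,000 trials per cell gives the same value and a type I error of 4.9% to 5.1%.

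| r (assumed) | 6 per arm | 12 per arm |
|---|---|---|
| 0.5 | 1.20 | 0.75 |
| 0.7 | 1.28 | 0.80 |
| 0.9 | 1.35 | 0.85 |
| Unadjusted | 1.29 | 0.85 |

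At high correlation ANCOVA gains nothing, and at 6 per arm with r = 0.9 it is slightly worse than the unadjusted difference.

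**6. Power for a 1.0 SD difference** (two-sided 0.05). Unadjusted: 34.7% at 6 per arm and 64.9% at 12. ANCOVA, for r from 0.5 to 0.9: 39.8% down to 32.7%, and 75.0% down to 64.7%. Unadjusted, 80% power needs a difference of about 1.80 SD at 6 per arm or 1.20 SD at 12.

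**The case against.** The strongest reply is that much of the text on the withdrawal phase is not shown. The SAS code announced in SAP 5.7.1 is absent, some of 5.7.2 and 5.7.3 and the exploratory objectives cannot be read, and SAP 5 says table templates are held separately. A treatment contrast could stand in any of these. This limits the point to what is stated, and it cannot be pressed to what is planned.

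For the same reason a reader might infer a stronger fault: that the five change-from-randomization models omit treatment, and so pool the arms or test each arm against zero. The documents do not support this. The terms listed in 5.7.1 belong to a model for single-arm data, and methods called similar may well add treatment when applied to randomized data. The separate columns in SAP 5 make pooling less likely.

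Second, upper limb tremor does have models after randomization. The combined score contains all six upper limb sub-items plus handwriting and spirals (SAP 4.9.1.3), Kinesia ONE scores the same tasks, and the Performance total includes the six sub-items. This stands: the gap in modelling is one clinician-rated score, not upper limb tremor as a whole.

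Third, SAP 7.1 reorders the endpoints of the duration objective to favour accelerometry and daily activities. This stands too, so the upper limb score should not be put ahead of that order.

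Fourth, Part B's primary objective is safety, the sample is one of convenience, and a reader can compute an unadjusted difference from each arm's n, mean and SD. This lowers the weight. It does not replace a contrast whose direction and covariate are fixed before unblinding, which is when SAP 1 says the plan will be final. The optional CIs in SAP 5 attach to descriptive statistics, and no between-arm interval is named.

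**Conclusion.** The point holds within the readable text. The clinician-rated TETRAS upper limb score has an MMRM for Part A and the Part B open-label phase only, gets descriptive statistics by arm after randomization, and no between-arm difference with CI is stated for the only randomized comparison. The treatment term in the other five models is an open question.

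This is a cheap improvement of minor to moderate weight. The estimate would be imprecise, with an unadjusted half-width of about 1.29 SD of change at 6 per arm and 0.85 at 12, so it cannot confirm an effect. Low between-arm power is no fault in a trial not sized for that comparison. The figures assume two-sided 0.05 and every participant randomized and assessed at Day 56. The ANCOVA figures also assume equal visit SDs and the stated correlations.

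**What to change.** In SAP 5.7.1, for the randomized withdrawal analysis set, add an ANCOVA of TETRAS upper limb change from randomization to Day 56, with randomized treatment as factor and the Day 42 post-dose value as covariate. Report the placebo minus PRAX-944 difference with its 95% CI. Higher scores mean more tremor, so a positive difference means more worsening on placebo. Leave Day 70 out of the contrast, since it closes the safety follow-up.

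If the code that is not shown already fits a treatment term, say so in the text and apply it to this score. Report the same contrast for the measures in 5.7.2.1, 5.7.2.2, 5.7.2.3, 5.7.2.5 and 5.7.2.6, and keep the endpoint order of SAP 7.1. Label all of it as estimation, not confirmation.

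The cost is SAP wording and one model per endpoint, with no new data or visits. The downside is a wide interval that readers may over-interpret in either direction, which is why the label matters.
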